DEMOGRAPHICS: Gender, date of birth, ethnicity, diagnoses, medications, current sports involvement (see Appendix 19 for demographics form). Questions from the International Study of Childhood Obesity, Lifestyle and the Environment survey (see Appendix 20) about the child's environment (e.g. accessibility of play areas) will also be collected [107].

FUNCTIONAL MOBILITY: The six-minute walk test for walkers [108] and the six-minute push test for non-walkers [109] (see Appendix 21).

Primary outcome measure

ISSUE IDENTIFICATION AND GOAL ATTAINMENT (CHILD REPORT):

Within-group change will be assessed using the Canadian Occupational Performance Measure (COPM) (see Appendix 22), which identifies the person-centred goal performance issues to improve, and assesses changes in occupational performance and satisfaction. Participant goal attainment will be assessed using Goal Attainment Scaling (GAS) (see Appendix 23), by defining five levels of goal attainment, thus ensuring that all attainment levels are mutually exclusive and measurable. This is an

Children and Teens in Charge of their Health: A feasibility study of solution-focused coaching to foster healthy lifestyles in children and young people with physical disabilities.

objective measure of behaviour change [110]. To minimize bias, GAS and COPM re-assessment will be conducted by a coach who has not worked with the child.

Secondary outcomes measures:

Between group change will be examined using the following measures:

BEHAVIOURAL ASSESSMENTS (CHILD REPORT):

Physical activity: The Habitual Activity Estimation Scale [111] (see Appendix 24) estimates time spent inactive, somewhat inactive, somewhat active, and very active, and shows good correlation with moderate to vigorous PA measured by accelerometry in our population ($p=0.02$) [112, 113].

Diet: The Dietary Screener Questionnaire (see Appendix 25) assesses dietary intake over the past 30 days and is validated against 24 hour multiple recall [114].

PSYCHOSOCIAL ASSESSMENTS (CHILD REPORT):

Self-determination: The *Arc's Self-Determination Scale* (see Appendix 26) has excellent reliability/validity with children with disabilities [64] and will assess self-determination to provide insight into potential mechanisms of behaviour change.

Self-efficacy: The *PA Self-efficacy Scale* (see Appendix 27) assesses confidence in the ability to be physically active when faced with challenges [115], with good internal consistency ($\alpha=.54-.71$) and test-retest reliability (ICC= .61-.82). High self-efficacy scores are significantly associated with greater moderate-vigorous physical activity [116]. *Self-efficacy for healthy eating* (see Appendix 28) assesses participants' feelings of competence for making healthy food choices in: social, emotional, and typical situations [117]. Higher scores are associated with healthy food intake ($\beta = .33, p < .01$), test-retest reliability (ICC= .80) [118].

BODY COMPOSITION (CHILD ASSESSMENT):

Children and Teens in Charge of their Health: A feasibility study of solution-focused coaching to foster healthy lifestyles in children and young people with physical disabilities.

Weight, height/length, waist circumference, and skinfold thickness (see Appendix 29 for record form) will be assessed, using standard guidelines [119].

Weight: Participants will be weighed minimally clothed (e.g. t-shirt, light shorts) without shoes to the nearest 100 grams using a chair scale.

Height: Those able to stand will be measured to the closest millimeter with a portable stadiometer or length measuring board. For those with severe contractures, careful segmental measurement will be conducted of the child's length in supine. Arm span and ulna length will also be measured as they offer useful proxies for length in children with lower extremity deformities [127, 128].

Body Mass Index (BMI): BMI will be calculated using both height and length as kilograms per meter squared (kg/m^2) and classified using Centres for Disease Control and Prevention cut-offs (85th–95th centile=overweight, above 95th percentile=obese) [120].

Waist circumference: Waist circumference (WC) has been shown to correlate well with fat mass as measured by dual-energy X-ray absorptiometry (DXA) [129-132] and has been specifically recommended for assessing body fat of children with SB [133] WC will be measured using a flexible tape measure at the narrowest level between the lower costal border and the iliac crest, over light clothing. Children with WC \geq 90th percentile have shown to be at higher risk of cardiovascular indicators [134, 135]. The RA will confirm lesion level using medical records and note any bulky masses, liposuction incision marks or spinal curvature.

Skinfold thickness: Skinfold thickness (SFT) is strongly associated with cardiovascular risk factors in children [136]. Tricep and subscapular skinfold thickness will be assessed, as per best practice [137] using Lange callipers (Cambridge Scientific Industries). Subscapular SFT in particular has

Children and Teens in Charge of their Health: A feasibility study of solution-focused coaching to foster healthy lifestyles in children and young people with physical disabilities.

previously demonstrated excellent test-retest reliability when conducted by skilled practitioners [127, 133]. The Slaughter equation will be used to assess body fat [138].

HOME AND ENVIRONMENT ASSESSMENT (PARENT REPORT):

The Family Eating and Activity Habits Questionnaire (see Appendix 30) is a 32-item parent-report assessment to assess the health behaviours of family members as well as the nature of the home environment [121]. It has high internal consistency (0.76-0.87) and test-retest reliability (0.75-0.89). These data will provide context for the children's behavioural outcomes, and allow us to examine the impact of the coaching on the family over time, which will also be examined in qualitative interviews with parents and children.

Post-Study

Following completion of the study, both child and their parent will be thanked and provided with a \$20 gift card for each visit (\$25 for the final visit) as a token of appreciation. Participants will also be offered volunteer hours. Families will be reimbursed for their parking expenses. Additionally, all participants who have completed all of the assessments will be entered into a prize draw for a gift card of \$150 at the end of the study. Participants and their parents will be asked if they wish to receive a summary of the research once the study is completed.

DATA ANALYSES

Sample characteristics will be summarized using descriptive statistics. Inferential statistics are not used in feasibility studies [82].

PRIMARY OBJECTIVE: Feasibility will be assessed using descriptive statistics using our *a priori success criteria* [82]. We will explore any sample/group differences between completers (complete Time 1 and Time 4 measures) and non-completers. We will also determine if there are sample and

Children and Teens in Charge of their Health: A feasibility study of solution-focused coaching to foster healthy lifestyles in children and young people with physical disabilities.

outcome variable differences between sites, disabilities and functional mobility, which will guide our target sample for the efficacy study.

Surveys completed by participants at Time 1 (all participants) and Time 4 (control group only) will be analyzed with descriptive statistics and thematic analysis [122]. Verbatim transcripts from **in-depth interviews** with the SFC-Peds group at Times 2 and 4 will undergo interpretative thematic analysis [123] informed by the phenomenological research tradition to identify acceptability of the intervention (e.g. satisfaction with coaching, perceived impact). Team members will independently code transcripts with a flexible, inductive coding system consistent with research objectives. Similar codes will be grouped, from which a consolidated list of master themes will be created that show patterns in participant experiences, supported by data. Characteristics (e.g. child age, gender, diagnosis and functional mobility) will be considered to understand the context of the participants' experiences. The research team will play a key role in data synthesis/interpretation. Code-recode, peer examination and team discussions will help establish trustworthiness.

Data from the **Photovoice** portion of the Time 4 in-depth interview will be read multiple times to embed the research team in the stories of the participants. The research team will code each transcript by noting words, phrases, or data segments that occur commonly in participant's narratives. Next, the research team will group these commonly occurring data segments into categories. At the next stage of analysis, the research team will perform this coding activity on each transcript. Subsequently, the research team will search accords the entire group of transcripts to develop commonly occurring categories and themes across the data set. The derived themes will be refined carefully. [name] will supervise the coding activity. The themes will be written into a thematic overview of how children with SP and CP see the body, health and physical activity from their own situated life worlds.

Children and Teens in Charge of their Health: A feasibility study of solution-focused coaching to foster healthy lifestyles in children and young people with physical disabilities.

SECONDARY OBJECTIVE: Measure responsiveness will be established by pre-post intervention differences using effect sizes (Cohen's *d*) and confidence intervals both within and between groups. It is well accepted to examine mean score changes for clinically significant differences pre and post intervention without calculating statistical significance (e.g. a score change of at least 2 points on the COPM is considered clinically significant [38]). We will therefore be able to assess the potential value of SFC-Peds over receiving printed materials only by examining goal scores over time. Our secondary outcomes will be compared with objective behaviour change (goal attainment) for concordance (e.g. whether successful goal attainment corresponds with increased self-determination). We will examine differences in outcome measures by disability, functional mobility, gender and age.

CHALLENGES

Our intervention (SFC-Peds) is largely virtual to reduce burden and enhance adherence [43]. All participants will receive gift cards for completing assessments to reduce attrition; this is a key feasibility outcome, especially in the control group. To reduce possible biases, participants will not meet during the study and coaches will not be involved in standard care. Standardized training (by 3 certified coaches) will be provided. Assessors will be asked which group they think participants are in; blinding success is indicated by accuracies at or below chance level. If adaptations are needed for the RCT, 'A process for Decision making after Pilot and feasibility Trials' (ADePT) [124] will be followed.

KNOWLEDGE TRANSLATION (KT)

A KT planning template [40] will ensure our findings have maximum reach yet are appropriate for feasibility study outcomes. The plan capitalizes on close collaboration of knowledge users and researchers within our investigative team. Integrated KT is promoted throughout the project by the involvement of clinical, family and knowledge user stakeholders, to ensure that the outputs meet the needs of the end users [125]. Holland Bloorview Research Family Engagement Committee members

Children and Teens in Charge of their Health: A feasibility study of solution-focused coaching to foster healthy lifestyles in children and young people with physical disabilities.

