Children and Teens in Charge of their Health: A feasibility study of solution-focused coaching to foster healthy lifestyles in children and young people with physical disabilities.

empathy and affirmative language [27, 69, 78, 79]. The resulting *intrinsic motivation* is associated with positive health behaviour changes [18]. Third, strategies used in SFC-Peds are tailored to the child's age, developmental stage, abilities and environmental settings, so that the same coaching *processes* can be used with a heterogeneous sample [27]. Finally, early pilot work by our team showed that children with physical disabilities (5 children with Duchenne muscular dystrophy) were able to engage with SFC-Peds and attained at least 1 PA or dietary goal after 12 weeks [80, 81]. The feasibility and acceptability of conducting a full RCT with a 12 month commitment remains unknown, however.

SIGNIFICANCE AND IMPACT OF THE RESEARCH

Physical, environmental and psychosocial restrictions mean that CWPD are adopting worrying PA and dietary habits. Despite this, we currently have limited evidence to inform interventions that may enhance lifelong health in CWPD. We suggest that a paradigm shift is needed, one that moves beyond traditional prescriptive programs to a strengths-based approach where intervention strategies enable new health habits to be integrated seamlessly into children and families' everyday lifestyles for long-term sustainability. Research such as our proposed study will ensure that this potentially transformative approach is rigorously examined and used in an evidence-based manner. As little is known about effective and acceptable behaviour change interventions for CWPD, this study's findings will make significant contributions to the field: i) Greater understanding of ecologically valid interventions that have the potential to enhance the long term health of CWPD; ii) Insight into how two different rehabilitation populations respond to SFC-Peds; and iii) Data on the responsiveness of outcome measures to a SFC-Peds intervention. These insights will enable us to design acceptable, feasible and rigorous interventions that will result in robust data for informing both research and clinical practice.

Children and Teens in Charge of their Health: A feasibility study of solution-focused coaching to foster healthy lifestyles in children and young people with physical disabilities.

OBJECTIVES & RESEARCH QUESTION

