Primary objective: To evaluate the feasibility (study design, methods, processes) and acceptability (family/child/clinician satisfaction, perceived usefulness) of conducting a RCT of a novel, brief, coaching intervention (SFC-Peds) for improving and sustaining PA and dietary habits in CWPD.

Secondary objective: To determine the responsiveness of selected outcome measures to SFC-Peds coaching over 12 months.

Principal research question: *“Is an efficacy trial to evaluate a six month SFC-Peds intervention to improve PA and dietary habits feasible to implement and acceptable to CWPD and families?”*

APPROACHES AND METHODS

Design: We will use a pilot RCT design [82] with two groups: One group (n=15) will work with a coach trained in SFC-Peds eight times over six months. The other group, the control group (n=15), will receive only standard printed materials at the start of the study. These materials will also be available to the SFC-Peds group to control for bias on study measures. The control group will allow us to control for information, maturation, repeated testing and attrition over the 12 month study [83]. All participants will receive standard care from existing clinicians who will not be delivering the SFC-Peds study intervention. The *feasibility* of trial processes, management, and resources will be assessed quantitatively. The *acceptability* of trial participation and coaching processes will be explored qualitatively. Qualitative enquiry lends insight into potential mechanisms of change and barriers to implementation and is therefore highly recommended when evaluating complex interventions [34].

Sample: Thirty children aged 10–18 inclusive and their parents who live within approximately two hours of Holland Bloorview Kids Rehabilitation Hospital (Toronto, ON) up to Thames Valley Children’s Centre (TVCC) (London, ON) will participate. The sites serve diverse socio-cultural communities.

Children and Teens in Charge of their Health: A feasibility study of solution-focused coaching to foster healthy lifestyles in children and young people with physical disabilities.

Child inclusion criteria:

- i) Between the age of 10 – 18 years inclusive
- ii) Diagnosis of SB or CP
- iii) Has physical capability to execute independent body movement with or without device
- iv) Cognitively able and willing to set PA or dietary goals
- v) Can communicate in English and respond to questions requiring some reflection and insight
- vi) Home internet connection

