- vii) Lives within 2 hours driving distance from Toronto up to London, Ontario OR willing to travel to either HB or TVCC for first in-person coaching session if randomized into coaching group

Child exclusion criteria:

- i) Surgery in past 6 months or upcoming 12 months that may impact PA or dietary intake (e.g. orthopedic surgery or neurosurgery)
- ii) Medical condition severely restricting diet
- iii) Underweight (less than fifth percentile)
- iv) Receiving specialist dietetic services

Parent inclusion criteria:

- i) Primary caregiver to a study participant
- viii) Can communicate in English and respond to questions requiring some reflection and insight

Sample size

Feasibility studies do not assess intervention efficacy and therefore do not require formal sample size calculations [33, 85]. The sample size ($n=30$) was set as a minimum needed to assess the key feasibility issues, as per feasibility best practices [86]. Fifteen SFC-Peds participants will suffice to show

Children and Teens in Charge of their Health: A feasibility study of solution-focused coaching to foster healthy lifestyles in children and young people with physical disabilities.

a tendency ($p < 0.10$) within the intervention group of behavioural change assessed by Goal Attainment Scaling (GAS; see ‘Outcomes’), equal to an effect size of 0.55 with a power of 0.80. The responsiveness of the secondary outcome measures will be compared with goal scores for evidence of concordance, e.g. a tendency of correlation between behavioural change and the Arc’s Self-Determination Scale. *Post hoc* estimates of variance will be key for the full trial’s design as they will inform the power calculations of the eventual RCT [85]. The sample size will allow us to assess recruitment success and show whether testing procedures, coaching goals and follow-up sessions are consistent across groups, mobility levels and sites. This sample size will also provide sufficient data for the qualitative work we are proposing to explore acceptability [87, 88].

Recruitment

We will recruit 15 children with SB and 15 children with CP (a total of 30 participants) and their parents from Holland Bloorview and TVCC.

Recruitment at Holland Bloorview

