Time 4 (SFC-Peds group): Children and their parents in the SFC-Peds group will undertake separate in-depth interviews facilitated by a qualitative interviewer to explore their experiences after coaching completion, perceived impact of intervention, barriers/facilitators to maintaining PA and dietary habits, and any unmet needs (see Appendix 16 for interview guide). Children will be asked to select 6-8 of their photographs taken since Time 2 to share with the interviewer. This will help remind children of their lifestyles in the previous six months, and enable them to speak in more depth about their feelings and experiences [106]. Each child will first be asked to explain why he/she took the photo, its meaning, what it shows of his/her coaching experience and the time since it ended.

Survey Time 4 (Control group only)

Time 4 (Control group): Children in the control group ($n=15$) will complete a Time 4 survey (see Appendix 17) regarding what they liked most/least about the study, any changes in health habits in the previous 12 months, acceptability of not getting the intervention, and tolerance of assessment protocols [30].

Qualitative Interview (Coaches only)

Time 4 (Coaches): Coaches will be interviewed to explore their experiences of delivering the intervention, e.g. challenges/facilitators, optimal coaching doses, use of technology (see Appendix 18).

Children and Teens in Charge of their Health: A feasibility study of solution-focused coaching to foster healthy lifestyles in children and young people with physical disabilities.

SECONDARY OBJECTIVE: *To determine the responsiveness of outcome measures to SFC-Peds coaching over 12 months.*

The following measures (excluding gender and date of birth) will be administered at Times 1, 2, 3, and 4 for all participants (approximately 1.5 hours duration). Issue identification and goal attainment measures are administered to SFC-Peds participants only with the first assessment conducted during the first coaching session. Measures have been selected based upon evidence of their responsiveness to change and psychometric properties in previous health promotion interventions [18]. Parent and child report questionnaires may be completed at home or online if the family prefers.

Participant characteristics

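### Does the p < 0.10 *tendency* clause in the sample-size section conflict with an analysis plan that rules out inferential statistics?

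*Combined protocol and SAP*

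**What the plan says.** The Sample size section says that feasibility studies need no formal sample size calculation and that the total of 30 "was set as a minimum needed to assess the key feasibility issues". It then adds what the coached arm of fifteen would be able to show: "a tendency ($p < 0.10$) within the intervention group of behavioural change", measured by Goal Attainment Scaling (GAS) and "equal to an effect size of 0.55 with a power of 0.80". The side, the test and the standardiser of the effect size are not given.

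The next sentence says that the secondary measures will be "compared with goal scores for evidence of concordance, e.g. a tendency of correlation between behavioural change" and a self-determination scale. No threshold is attached there.

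Data Analyses opens with "Inferential statistics are not used in feasibility studies". For the secondary objective it plans Cohen's d with confidence intervals, within and between groups, at no stated level. It defends judging mean score change without significance tests. It describes concordance only by example: whether children who attain their goals also gain in self-determination.

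The secondary objective is "To determine the responsiveness of selected outcome measures to SFC-Peds coaching over 12 months". Under the study assessments for that objective, "Issue identification and goal attainment measures are administered to SFC-Peds participants only", so any comparison with goal scores rests on at most fifteen children.

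**The concern.** One section quotes a p-value and a power; another says that no inferential statistics will be used. If p < 0.10 is a rule for labelling results, three things are open.

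- **Side.** At n = 15 the side decides whether the quoted power is right.
- **Scope.** The word *tendency* comes back one sentence later for the concordance correlation, so a reader may carry the threshold over to an analysis that the power figure does not cover.
- **Replacement.** If Data Analyses overrides the threshold, it names no coefficient, time point or way of reading concordance.

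At stake is part of the secondary objective. The Significance section lists "Data on the responsiveness of outcome measures to a SFC-Peds intervention" as one of three contributions of the study. The same observed correlation might be called a tendency by one analyst and not by another.

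**Working it through.** **Inputs.** From Sample size: n = 15, effect size d = 0.55, power 0.80, threshold 0.10. Not stated, so assumed: d is the mean change divided by the SD of change, and the test is a one-sample (paired) test.

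**1. Reproduce the plan's figure, one-sided 0.10.**

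- Normal approximation: n = ((1.2816 + 0.8416) / 0.55)² = 14.9, which rounds up to 15.
- Power at n = 15: Φ(0.55 × √15 − 1.2816) = Φ(2.130 − 1.282) = 0.802.
- Paired t on 14 df (noncentral t): 0.784.

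The stated n and power are met.

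**2. The same inputs, two-sided 0.10.**

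- Normal approximation: n = ((1.6449 + 0.8416) / 0.55)² = 20.4, so 21.
- Power at n = 15: Φ(2.130 − 1.645) = 0.686; paired t, 0.648.

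The figure therefore has one natural reading, one-sided 0.10. The side is unwritten but can be recovered from the numbers.

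**3. What carrying the threshold over to concordance would do.** This assumes a Pearson correlation of change scores tested at 0.10, which the plan does not state. The smallest r that passes is t / √(13 + t²):

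| Reading | t (13 df) | Smallest r |
|---|---|---|
| One-sided | 1.350 | 0.35 |
| Two-sided | 1.771 | 0.44 |

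An observed r of 0.40 gives t = 0.40 × √13 / √(1 − 0.16) = 1.574, so p = 0.070 one-sided and 0.140 two-sided. The label would change with the side. The estimate would not: r = 0.40, with a Fisher-z 95% interval of tanh(0.424 ± 1.96 / √12), that is −0.14 to 0.76. Reported that way, as Data Analyses already reports change, it needs no label and shows plainly how little fifteen children can say.

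**4. Set the sections side by side.**

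| Item | Sample size | Data Analyses | Conflict for the analyst? |
|---|---|---|---|
| Basis of n = 30 | Feasibility | – | No |
| GAS change | What n = 15 can show at p < 0.10 | Cohen's d with interval | No: only the second says how to report |
| Concordance | Correlation, as an example; no threshold | Example only; no statistic named | No: a descriptive correlation fits both |

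Data Analyses itself plans confidence intervals, so its opening sentence is best read as ruling out hypothesis tests, not every measure of uncertainty. A correlation coefficient is compatible with that.

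**The case for a change.** The strongest case for a change is that concordance is a planned analysis under a stated objective, yet neither section gives its coefficient, measures, time point or reading. The word *tendency* was tied to p < 0.10 one sentence before it was used again. Two competent analysts could present the result differently, and deleting a clause and adding two sentences would cost nothing.

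What stands is that the detail is thin and the p-value clause sits awkwardly beside the opening of Data Analyses. Tidying both would be harmless. Three further steps do not stand.

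- **That the p < 0.10 threshold is reused.** This is an inference from one repeated word. The concordance sentence states no p-value, and *tendency* can be plain English there.
- **That a criterion is missing.** An exploratory correlation in fifteen children is better reported without a cut-off. The natural remedy would also report an estimate and an interval with no yes/no label, so the lack of a cut-off is not a defect.
- **That false positives would be frequent.** Testing seven to nine secondary measures at 0.10 with no true association would give at least one *tendency* with probability 1 − 0.9⁷ = 0.52 to 1 − 0.9⁹ = 0.61, if the tests are independent. The plan does not describe such testing, and the measures are unlikely to be independent: BMI, waist and skinfolds overlap. With an assumed correlation of 0.5 between measures, simulation gives about 0.35 to 0.48; with 0.7, about 0.28 to 0.37. None of these figures describes the plan as written.

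**Conclusion.** No change is needed. The quoted power is sound as a one-sided 0.10 within-group calculation (0.80 normal, 0.78 paired t), provided that the effect size is mean change over the SD of change. It would fall to 0.69 or 0.65 only under a two-sided reading, which the plan's own numbers do not support. The clause illustrates sensitivity; it neither sets the sample size nor prescribes a test.

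Data Analyses tells the analyst what to report for goal change, and a descriptive correlation fits both sections for concordance. What is missing (side, coefficient, time point, interval level) is detail that an analyst would fill sensibly. Supplying it would leave n = 30, the feasibility criteria and every estimate as they are. This conclusion assumes that Data Analyses governs reporting; if the team did mean to label correlations at p < 0.10, the dependence on side shown above would apply.

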Coaching will be guided by a framework developed by SFC-Peds clinicians at Holland Bloorview to integrate the Canadian Occupational Performance Measure (COM) and Goal Attainment Scaling (GAS) outcome measures into SFC-Peds (see Appendix 8 for framework). The **first coaching session** will take place in the family's home to establish rapport. Parents play an important supportive role in the coaching process, although the level and type of support they provide will be customized to the age and abilities of their child. SFC-Peds is ideal for establishing 'common ground' between children and parents so that they are working towards goals that they both deem important, maximizing the chances of sustainability. To enhance child self-determination, the coach will first support the child to identify their 'preferred future,' i.e. the 'big picture' the participant wants to work towards in the context of health habits. Then, the child, parent and coach will co-create actionable goals to help children to work towards it. Focusing upon goals that are personally meaningful to the child fosters autonomy [94]. The coach and parents will then support the child to identify realistic, real-world goal attainment strategies using their own strengths and resources, supporting the development of competence. The use of active listening, empathy and attentive body language creates a trusting relationship, and promotes a sense of relatedness [95]. Parental involvement in the coaching sessions will ensure that goals and goal-attainment strategies are realistic for the child, his/her environmental settings and the family. For example, if the parent cannot transport a child to an organized activity to meet their physical activity goal, then a different strategy would be co-created that is appropriate for the

Children and Teens in Charge of their Health: A feasibility study of solution-focused coaching to foster healthy lifestyles in children and young people with physical disabilities.

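### The goal-attainment tendency that justifies 15 coached children is a test against zero change with no control scores, so it cannot show value over printed materials

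*Combined protocol and SAP*

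**What the plan says.** **Sample size.** The section first says that a feasibility study needs no formal calculation. It then gives one: "Fifteen SFC-Peds participants will suffice to show" "a tendency ($p < 0.10$) within the intervention group of behavioural change assessed by Goal Attainment Scaling", "equal to an effect size of 0.55 with a power of 0.80". It names no test, sidedness or reference value.

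**Intervention implementation.** In the first coaching session, "the child, parent and coach will co-create actionable goals".

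**Study Assessments, secondary objective.** "Issue identification and goal attainment measures are administered to SFC-Peds participants only with the first assessment conducted during the first coaching session". Control children therefore have no goal scores at any time.

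**Primary outcome measure.** GAS and the Canadian Occupational Performance Measure (COPM) are listed together. GAS works "by defining five levels of goal attainment, thus ensuring that all attainment levels are mutually exclusive and measurable". The level at which a child starts is not stated.

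**Design.** The control group is there to account for information, maturation, repeated testing and attrition.

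**Data Analyses.** The opening paragraph says inferential statistics are not used in feasibility studies. The secondary-objective paragraph plans Cohen's d with confidence intervals, within and between groups. It then concludes that goal scores over time will let the team assess what coaching adds to printed materials alone. It also uses goal attainment as the yardstick for the secondary outcomes.

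**The concern.** A within-group change from baseline supports a claim about an intervention only if no change is what would be expected without it. That is doubtful for a goal chosen by a child who was enrolled because of willingness to set one. The goal is scored when it is created, presumably because it is not yet met. The child then has six months, printed advice and standard care as well as coaching, so some upward movement is plausible whether or not coaching works.

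The control arm was included to account for such influences, but it cannot do so for a measure it never receives. The conclusion written into Data Analyses, that goal scores speak to value over printed materials, therefore has no comparison behind it. If the plan is followed as written, ordinary progress will be credited to coaching when the case for the full trial is made. The stated effect size and power also lend the goal measure a formal weight that the design does not give it.

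**Working it through.** **1. Reproduce the stated power.** Inputs from Sample size: n=15, standardised effect d=0.55, alpha=0.10. For a one-sample test of change against zero, normal approximation, power = Φ(d√n − z), with d√n = 0.55 × 3.873 = 2.130.

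| Reading | Calculation | Power |
|---|---|---|
| One-sided, normal | Φ(2.130 − 1.282) | 0.802 |
| One-sided, noncentral t | 14 df | 0.784 |
| Two-sided, normal | Φ(2.130 − 1.645) | 0.686 |
| Two-sided, noncentral t | 14 df | 0.648 |
| Two-sample 15 v 15, one-sided | | 0.59 |
| Two-sample 15 v 15, two-sided | | 0.44 |

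Only the one-sided within-group test against zero gives about 0.80, so zero change is the reference the plan was powered on.

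**2. What that test can be satisfied by.** Assumptions, none stated in the plan: one goal per child, each gainer moves one level, all others change by exactly zero, paired t-test. With k gainers, mean = k/15, variance = (k − k²/15)/14, and t = mean/(SD/√15).

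For k=2: mean 0.133, SD 0.352, t = 0.133/0.0909 = 1.468, one-sided p=0.082.

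The required number depends on the test:
- one-sided t: 2 of 15 (p=0.082)
- two-sided t: 3 of 15 (p=0.082)
- exact sign test: 4 of 15 one-sided or 5 of 15 two-sided (p=0.0625 each)
- one-sided t with one child a level worse: 4 gainers (p=0.094); 2 gainers then give p=0.29

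**3. How often it would be met with no coaching effect.** Let q be the share of children who would gain a level anyway. The documents give no value, so q is assumed and shown over a range. With no decliners, the one-sided t-test is met with probability 1 − (1−q)^15 − 15q(1−q)^14.

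| Assumed q | One-sided t (2 or more gain) | Two-sided t (3 or more gain) |
|---|---|---|
| 5% | 17% | 4% |
| 10% | 45% | 18% |
| 20% | 83% | 60% |

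For q=10%: 1 − 0.206 − 0.343 = 0.451. The chance passes 50% at q of about 11% (one-sided) or 17% (two-sided). If children can also fall a level, the one-sided figure is lower by simulation: 52% with 20% up and 5% down, 33% with 20% up and 10% down, and 11% with 20% each way.

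**4. Does the planned interval avoid the problem?** No. A within-group confidence interval is also read against zero. In the same setting, 4 of 15 gaining one level gives mean 0.267, SD 0.458, d = 0.58, and a 95% interval with lower limit 0.267 − 2.145 × 0.118 = 0.013, which excludes zero.

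**5. The sections side by side.** Sample size relies on a p-value, while Data Analyses excludes inferential statistics. Study Assessments restricts GAS and COPM to the coached arm, while Data Analyses uses goal scores for a statement about coaching versus printed materials. Neither pair can stand as written.

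**The case against.** The strongest reply is that this is not an operative rule. The p-value appears only in the sample-size rationale, the analysis section disclaims testing, and the tendency is not among the feasibility success criteria. No progression decision hangs on it. All of that stands. A reader might infer that a met tendency would trigger the full trial; the documents do not say so. The reply does not remove the problem, because the conclusion about value over printed materials sits in the analysis plan itself, where the disclaimer also is.

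Other stronger readings also go further than the documents allow:

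- *Two of 15 children always suffice.* This holds only for a one-sided t-test with equal steps and no decliners. The plan names no test and allows more than one goal per child.
- *The test would usually be met without any coaching effect.* This needs an uncoached gain rate above about 11% with no decliners, and the documents give no rate.
- *Children start at the floor of the scale.* That a new goal is unattained is a reasonable inference, but the starting level and the room to worsen are not stated, and the GAS form is in an appendix not available here.
- *An effect of 0.55 means about three-quarters of children have not moved.* This is true only if changes are 0 or 1 (3 or 4 gainers give d=0.48 or 0.58). Three children at +2, six at +1, three at 0 and three at −1 give d = 0.6/1.056 = 0.57 with only 3 of 15 unchanged.
- *The plan has no other numerical reference for its primary measures.* It cites a 2-point change on the COPM as clinically significant. That threshold does not supply a comparator, since controls have no COPM scores either.

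**Conclusion.** The concern holds in limited form. The stated power is that of a one-sided test of coached children against zero change, and zero is not a meaningful reference for a goal scored as it is created. With goal scores in one arm only, no analysis of them can separate coaching from maturation, printed information or ordinary progress. The statement about value over printed materials is therefore unsupported, and the p-value contradicts the analysis section. These conclusions need no assumption beyond the text, except that a newly set goal is not yet attained.

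The size is illustrative. The 17% to 83% range in the one-sided column rests on assumed uncoached gain rates of 5% to 20%, one-level gains and no decliners; a two-sided test or any decline lowers it. The figures show how sensitive the test is to ordinary progress and do not predict how often it would mislead. This is worth correcting before analysis, but it does not undermine the feasibility criteria, which do not use goal scores.

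**What to change.** **Sample size.** Remove the p<0.10 test, the effect size and the power. State instead the precision that 15 children give for the proportion of allocated coached children at or above the expected goal level at Time 2, with an exact 95% interval; for example, 8/15 = 53%, interval 27% to 79%. Say in advance which of the five levels counts as expected and how a child without a Time 2 score is counted.

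**Data Analyses, secondary objective.** Report that proportion beside the Cohen's d and interval already planned. State that goal-score change is a descriptive, uncontrolled within-group result and does not show value over printed materials. Base between-group statements only on measures collected in both arms.

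These edits also remove the conflict with the statement that inferential statistics are not used. No pass/fail threshold is needed: it would require an uncoached rate that this trial cannot supply.

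**Cost.** Protocol wording and one descriptive table from data already collected. The drawback is that a wide interval replaces a favourable power claim.
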